10.6.4 Subject Death

Subject deaths must be reported to Respicardia or designee within 24 hours of investigator knowledge, and the site must also complete an Adverse Event CRF.

If a subject death occurs while the subject is in the hospital, submit a copy of the hospital discharge note(s) and/or progress note(s) related to the death and/or death summary to Respicardia, Inc. If an autopsy is performed, submit a copy of the autopsy report and once the death certificate becomes available, send a copy to the Sponsor within 10 days. If a subject death occurs at a site remote from the investigational site, it is the investigative site's responsibility to make an attempt to retrieve all pertinent information related to the subject's death and submit the PI's summary of the known events surrounding the death. In all cases

following subject death, the investigator should request that the **remēdē** System be explanted and returned to Respicardia, Inc.

10.7 Protocol Deviations

A protocol deviation is defined as an instance(s) of failure to follow, intentionally or unintentionally, the requirements of the CIP, including the Investigator Agreement, IRB/IEC, or local regulatory requirements.

The PI must maintain accurate, complete and current records, including documents showing the dates of and reasons for each deviation from the protocol. Protocol deviations must be reported to Respicardia, Inc. regardless of whether or not medically justifiable. In the event the deviation involved a failure to obtain a subject's consent, or is made to protect the life or physical well-being of a subject in an emergency, the deviation must be reported to Respicardia, Inc. and the IRB/IEC within 5 working days of the deviation occurring. All other deviation reporting to IRB/IEC must comply with local IRB/IEC and local regulatory requirements.

Respicardia, Inc. will be responsible for analyzing, assessing and trending deviations to determine if corrective or preventive action is required. All deviations will be reported in the progress and final study reports.

10.8 Adverse Events

All adverse events (AEs) that occur between the subject signing the ICF and study exit will be documented in a timely manner and reported to the Sponsor. The investigator at the site should follow AEs until they have resolved, the condition has stabilized, or the subject exits the trial and report such follow-up information to the sponsor. AEs will be recorded in detail on the AE CRF.

In addition, serious AEs, implant-related AEs, therapy-related AEs, and device-related AEs occurring after exit from the pivotal trial and prior to signing ICF in this trial will be collected.

An independent Clinical Events Committee (CEC) will adjudicate, at minimum, all serious adverse events, including deaths, and therapy-, device- or implant-related adverse events.

CEC membership will include at least one physician from each of the following specialties: sleep, cardiology (preferably heart failure), and electrophysiology (familiarity with device implant procedures).

Definitions and Classifications

Adverse event (AE): Any untoward medical occurrence, unintended disease or injury, or untoward clinical sign (including abnormal laboratory findings) in subjects, users or other

persons, or resulting in abandonment of **remedē** System therapy, whether or not related to the **remedē** System or study procedures. For users or other persons, this definition is restricted to events related to the **remedē** System.

Procedure-related: An adverse event (whether serious or not) that occurs due to any procedure required to implant, revise, or explant the **remedē** System.

Device-related: An adverse event (whether serious or not) that is related to the **remedē** System and includes device explant due to device-related infection and events such as: device malfunction, lead fracture, lead component failure, lead dislodgment, lead displacement, pocket perforation, or extra-respiratory sensation requiring lead revision.

Battery depletion within an expected timeframe and resulting IPG replacement will be reported as a system modification and not an adverse event, unless the battery depletion occurred earlier than expected in which case it will also be recorded as an AE.

Therapy-related: An adverse event (whether serious or not) that includes events such as diaphragmatic stimulation discomfort, extra-respiratory stimulation, or concomitant device interaction.

Anticipated Adverse Event: An adverse event for which the nature, severity, or degree of incidence is known and identified in the product labeling or CIP.

Possible adverse effects include, but are not limited to, the following:

Implant Procedure-Related

- Adverse contrast dye reaction such as allergic reaction, pulmonary edema, or worsening renal function
- Adverse reaction to radiation exposure
- Thromboembolism
- Air embolism
- Bleeding
- Cardiac perforation including tamponade
- Hematoma, seroma, local bruising or swelling
- Hypotension
- Local wound healing issues at device implant site including wound dehiscence, pocket erosion, extrusion, movement of implanted device, keloid formation
- Pneumothorax
- Hemothorax
- Vascular damage, e.g., venous dissection, perforation

Lead and System-Related

- Adverse biocompatibility reaction to the implanted system
- Infection
- Lead breakage
- Lead dislodgement
- Lead not connected or secured appropriately in device header
- Implantable device malfunction
- Requirement for more energy to stimulate the nerve or ineffective stimulation
- Venous occlusion

Therapy-Related

- Crosstalk with another implanted device
- Disrupted sleep
- Muscle fatigue or discomfort in diaphragm, chest or abdomen from appropriate stimulation
- Nerve dysfunction
- Perturbation of blood gases causing hypoxia, hypercapnea and/or hypocapnea
- Inappropriate sensations
- Worsening heart failure, respiratory status or overall health

Other Procedure, System or Therapy-Related

- Anxiety
- Arrhythmia, including ventricular fibrillation
- Death
- Depression
- Hypotension
- Pain
- Skin irritation or local allergic reaction
- Thrombus or embolism, potentially leading to pulmonary embolism or stroke

Serious Adverse Event (SAE): Any adverse event as defined above (whether anticipated or unanticipated) that:

- led to a death,
- led to a serious deterioration in the health of the subject that
 - resulted in a life-threatening illness or injury,
 - resulted in a permanent impairment of a body structure or a body function,
 - required inpatient hospitalization or prolongation of existing hospitalization,
 - resulted in medical or surgical intervention to prevent permanent impairment to body structure or a body function, or
- led to fetal distress, fetal death or a congenital abnormality or birth defect

In addition, the following will be considered an SAE for purposes of this trial:

- A device or therapy related AE that required a system modification (excluding IPG replacement for battery depletion within anticipated timeframe or elective explant)

Unanticipated Adverse Device Effect (UADE): any serious adverse effect on the health or safety or any life-threatening problem or death caused by, or associated with, a device (**remēde** System), if that effect, problem, or death was not previously identified in nature, severity, or degree of incidence in the product labeling, or any other unanticipated serious problem associated with a device that relates to the rights, safety, or welfare of subjects. Investigators must report any suspected UADE to the sponsor as soon as possible but no later than ten (10) working days of knowledge of the event. Respicardia, or designee, will report results of any UADE evaluation to FDA and to all reviewing IRBs/IECs and participating investigators within ten (10) working days after Respicardia first receives notice of the effect.

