7 STUDY OBJECTIVES

1. Evaluate the survival rate

This endpoint is an assessment of survival in subjects with moderate to severe CSA being treated with the **remedē** System. Survival will be compared to historical controls or newly published results at three and five years post implant. No formal statistical hypothesis will be tested.

2. Evaluate long-term three and five-year device-related Serious Adverse Events (SAEs)

This endpoint is an assessment of long-term safety via summary of anticipated or unanticipated device-related SAEs. Events must meet the definition of serious as defined in [Section 10.8](#). Device-related SAEs include device explants due to device-related infection and events such as: device malfunction, lead fracture, lead component failure, lead dislodgment, lead displacement, pocket perforation, or extra-respiratory sensation requiring lead revision. **remedē** System IPG replacement for battery depletion will not be considered a device-related SAE unless it is earlier than anticipated. The number of events and subjects with an

event will be summarized through each time point. No formal statistical hypothesis will be tested.

3. Evaluate long-term three and five-year therapy-related SAEs

This endpoint assesses the safety of the **remedē** System by evaluating anticipated or unanticipated therapy-related SAEs. Therapy-related SAEs must meet the definition of a SAE as defined in [Section 10.8](#) and include events such as diaphragmatic stimulation discomfort, extra-respiratory stimulation, or concomitant device interaction. The number of events and subjects with an event will be summarized through each time point. No formal statistical hypothesis will be tested.

4. Evaluate the AHI, CAI, and obstructive apnea index (OAI) at three years using in-home polygram (PG) and at five years using in-lab polysomnogram (PSG)

This effectiveness endpoint will be assessed by summarizing the AHI, CAI, and OAI at three and five years, as well as change from baseline at five years. No formal statistical hypothesis will be tested.

5. Evaluate the change in quality of life from baseline to three and five years using the ESS

The ESS is a validated instrument that assesses a subject's daytime sleepiness. The objective is to demonstrate a reduction in the ESS score from baseline at three and five years. No formal statistical hypothesis will be tested.

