10.5 System Modifications

In the event the **remedē** System requires modification (i.e., lead repositioning or replacement, system explant, or IPG replacement) the following assessments should be performed:

- Adverse Event review and reporting
 - Review events with subject and review medical records since last visit
- Concomitant device interaction testing, if applicable

In addition, system modifications occurring after exit from the pivotal trial and prior to signing ICF in this trial will be collected.

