10.8.1 Safety Endpoint Definitions

Serious device-related: For the purpose of assessing the device-related safety endpoint, a serious device-related adverse event is an event that meets the definition of serious and includes device explant due to device-related infection and events such as: device malfunction, lead fracture, lead component failure, lead dislodgment, lead displacement, pocket perforation, or extra-respiratory sensation requiring lead revision.

Serious therapy-related: For the purpose of assessing the therapy-related safety endpoint, the event must meet the definition of serious and include events such as diaphragmatic stimulation discomfort, extra-respiratory stimulation, or concomitant device interaction.

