11 STATISTICAL METHODS

11.1 General Statistical Considerations

Data from this study will be combined with data from the **remedē** System Pivotal Trial. All subjects will be pooled for analysis regardless of original randomization assignment.

Descriptive statistics will be used to summarize data. Continuous variables will be summarized using means, standard deviations, medians, interquartile ranges, minimums and maximums. Categorical variables will be summarized by calculating the percent of subjects in each category. No imputation for missing data will be performed.

Statistical analyses will be performed using validated software (e.g., SAS).

Copies of databases used to prepare clinical report summaries will be archived to enable any statistical analyses performed to be replicated.

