11.3 Data Analyses

All subjects randomized in the **remedē** System Pivotal Trial will be included in the safety assessments, unless otherwise noted. All adverse events will be summarized by seriousness, relatedness, and temporal relationship to the procedure and will be analyzed in a descriptive fashion. The number of events and number of subjects experiencing events will be summarized.

The survival distribution will be estimated with a Kaplan-Meier curve and the 95% confidence interval for the three and five year (or other time point of interest) survival rates will be calculated using the standard error determined by the Peto method.¹ The survival rate will be compared to historical controls and/or newly published results.

Subjects with follow-up data at the visit of interest will be included in the effectiveness assessments. Change from baseline analyses will include subjects with baseline and follow-up visit data.

Additional exploratory and/or subgroup analyses may also be performed to characterize study outcomes.

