The primary effectiveness endpoint was a comparison of the proportions of patients in the treatment versus control groups achieving a reduction in AHI of $\geq 50\%$ from baseline to 6 months. The primary safety endpoint was freedom from serious adverse events associated with the implantation procedure, the system, or delivered therapy in the combined study groups through 12 months. A serious adverse event was defined as any adverse event that led to death, led to a serious deterioration in the health of the subject, resulted in a life-threatening illness or injury, resulted in a permanent impairment of a body structure or a body function, required inpatient hospitalization or prolongation of existing hospitalization, resulted in medical or surgical intervention to prevent permanent impairment to a body structure or a body function, or led to fetal distress, fetal death or a congenital abnormality or birth defect.

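### Do the pooled three- and five-year SAE counts need a written step to re-classify pivotal-trial events under Section 10.8?

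*Combined protocol and SAP*

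**What the plan says.** Section 7 sets the counting rule. For device-related SAEs (Objective 2), "Events must meet the definition of serious as defined in" Section 10.8, and Objective 3 carries the same condition for therapy-related SAEs. Both are tallied cumulatively at three and five years, without a hypothesis test.

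Section 10.8 lists the usual seriousness criteria and then adds, for this trial, "A device or therapy related AE that required a system modification", leaving out elective explant and IPG replacement for expected battery depletion. Section 10.5 describes a modification as "lead repositioning or replacement, system explant, or IPG replacement". Section 10.8.1 restates that a device-related endpoint event must be serious, and that the category "includes device explant due to device-related infection and events such as" device malfunction, lead dislodgment and lead displacement.

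Section 11.1 begins "Data from this study will be combined with data from the" pivotal trial. Section 11.3 puts every randomized pivotal subject in the safety assessments and asks for adverse events by seriousness, relatedness and timing relative to the procedure: "The number of events and number of subjects experiencing events will be summarized".

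Under Section 10.8 the events committee "will adjudicate, at minimum, all serious adverse events, including deaths, and therapy-, device- or implant-related adverse events". The adverse event form in Appendix C has an event type for updating an event first reported in the pivotal trial, and the same form carries the system-modification box.

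The pivotal definition appears only in the device manual, Appendix F, Section 1.9.3: "A serious adverse event was defined as any adverse event that led to death", followed by the remaining standard criteria. System modification is not among them.

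**The concern.** A cumulative count from implant to five years mixes events flagged during the pivotal trial with events flagged under this protocol. If the pivotal flags were copied across unchanged, a related event that led to a lead revision could be non-serious in the early period and serious in the late one. The totals would then depart from the definition that Objectives 2 and 3 require, and part of any contrast between early and late years would come from the change of rule.

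The pivotal tables seem to offer examples. Lead dislodgement and displacement appear among both the serious events (Table 3) and the non-serious events (Table 4). Both serious implant-site infections are attributed to the procedure and none to the system, while Table 5 lists two explants for implant-site infection. Those tables also count only probable or definite relatedness, whereas the new form adds a possible grade and the plan names no cut-off for the combined tables. Because nothing is tested, these counts are the whole result for both safety objectives.

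**Working it through.** **1. Reproduce the published figure.** Appendix F, Table 2 gives 138 of 151 subjects free from related SAEs through 12 months, 91% with exact interval 86% to 95%. The exact interval has lower limit Beta⁻¹(0.025; x, n − x + 1) and upper limit Beta⁻¹(0.975; x + 1, n − x). With x = 138 and n = 151, 138/151 = 91.4%, interval 85.7% to 95.3%. This agrees.

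**2. Check the table rows.**
- Table 3, system-related SAEs: pocket erosion 1 + dislodgement 2 + device interaction 1 + component failure 1 + displacement 1 = 6.
- Table 3, therapy-related SAEs: device interaction 1 + extra-respiratory stimulation 1 = 2.
- Table 4, non-serious system-related: stimulation discomfort 1 + impedance 3 + thresholds 2 + programming error 1 + venous thrombosis 2 + dislodgement 1 + displacement 1 = 11.

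All three sums match the printed totals.

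**3. Size under stated assumptions (12 months, n = 151, separate subjects).**
- System-related as reported: 6/151 = 4.0% (exact 95% interval 1.5% to 8.4%).
- If the one non-serious dislodgement and the one displacement both needed a modification: (6 + 2)/151 = 8/151 = 5.3% (2.3% to 10.2%). The shift is 2/151 = 1.3 percentage points.
- Therapy-related as reported: 2/151 = 1.3% (0.2% to 4.7%). Each further subject adds 1/151 = 0.7 points.

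Re-flagging all 11 non-serious system-related events would give 17/151 = 11.3%. That would require a programming error, two venous thromboses and a stimulation-discomfort event all to have needed a modification. Nothing in the documents supports this, so I do not treat it as a plausible ceiling.

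**4. Which definition governs pivotal events?** Section 7 and Section 10.8.1 attach the Section 10.8 definition to the endpoint, whatever the period in which the event was collected. Section 11 brings pivotal subjects and data into that endpoint. Together they leave one rule for the whole count.

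**5. Does the mix of serious and non-serious lead events show a mismatch?** No. Appendix F, Section 1.12.8.1 describes repositioning when capture cannot be regained by programming other electrodes, so some displacements involve no modification and would be non-serious under either definition. The pivotal criteria also include surgical intervention to prevent permanent impairment, and hospitalization, which could already capture revisions. The one lead component failure is serious in Table 3, none appears in Table 4, and Table 5 lists one explant for that cause. This fits events needing modification having already been serious, although matching the tables is an inference.

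**6. The infections.** Section 10.8.1 speaks of explant for device-related infection, and Section 10.8 defines procedure-related events separately. Attributing both serious infections to the procedure is compatible with that. Both are already SAEs within the 13 related events, and Section 11.3 would tabulate them by seriousness and relatedness in any case.

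**The case for a change.** The best case for a change is that a governing definition is not a procedure. No sentence tells anyone to return to the pivotal records. The trial-specific wording of the extra item could be read as covering only events after new consent. The adjudication clause follows text about events after consent and in the gap between studies. The form's update option reaches only re-consented subjects, at most 94, so at least 151 − 94 = 57 of the randomized subjects (57/151 = 38%) lie outside it, and a resolved event would prompt no update. Section 10.8.1 also places extra-respiratory sensation requiring lead revision under device-related events, while the pivotal tables put extra-respiratory stimulation wholly under therapy. On a base of six events, two re-flagged subjects would be a rise of one third.

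Part of this stands. The operational step is unwritten, the update option is a partial route only, and the relatedness cut-off for the combined tables is unstated. But the restrictive reading sets aside Objectives 2 and 3, which exempt no pivotal events from the endpoint definition. The claimed difference between definitions rests on one condensed sentence in a device manual, since the pivotal protocol is not among the documents. On relatedness, the pivotal tables supply a precedent (probable or definite), and the form records each grade separately, so any cut-off can be applied and shown.

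**Conclusion.** No change to the plan is needed. The endpoint definition is stated, it covers the pooled period, and checking pivotal device- and therapy-related events against it from existing records is work that an analyst would put in the table specifications. The same goes for using one relatedness cut-off throughout.

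The size of any discrepancy cannot be computed, because the documents do not say which pivotal events led to a modification. It may be zero. The illustration of 4.0% against 5.3% assumes that both non-serious lead events needed a modification, occurred in subjects not already counted, and were not in fact handled under the pivotal criteria. Even then the 1.3-point shift lies well inside the exact interval for the reported figure (1.5% to 8.4%), and no test, threshold or planned early-versus-late comparison depends on it.

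This conclusion assumes that the analysts apply Sections 7 and 10.8.1 as written. If the final report carried the pivotal seriousness flags forward without checking them, that would be a departure from the plan rather than a fault in it.

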10.8.1 Safety Endpoint Definitions

Serious device-related: For the purpose of assessing the device-related safety endpoint, a serious device-related adverse event is an event that meets the definition of serious and includes device explant due to device-related infection and events such as: device malfunction, lead fracture, lead component failure, lead dislodgment, lead displacement, pocket perforation, or extra-respiratory sensation requiring lead revision.

Serious therapy-related: For the purpose of assessing the therapy-related safety endpoint, the event must meet the definition of serious and include events such as diaphragmatic stimulation discomfort, extra-respiratory stimulation, or concomitant device interaction.

